14. Daunorubicin Dosing (Induction only): Daunorubicin will be given at a dose of 60 mg/m² as an IV in combination with cytarabine and PF-04449913, on Days 1-3 of induction Cycle 1. Induction chemotherapy may be repeated for one additional cycle if an unsatisfactory clinical response is observed and there are no signs of cardiac toxicity. If clinical signs of cardiac dysfunction are observed, a repeat MUGA/ECHO should be performed, and must demonstrate a LVEF ≥45% to receive a second course of induction chemotherapy. If a second cycle of induction therapy is required, it may start prior to Day 28 of induction Cycle 1 but not earlier than Cycle 1/Day 21. Dose must be recalculated if the weight changes by >10%.
15. Cytarabine Dosing: Separate cytarabine dosing and schedules will be used for Induction and Consolidation and administered using institutional guidelines:
Induction: Cytarabine will be administered (in parallel to daunorubicin) at a dose of 100 mg/m² by continuous IV infusion for 7 days on Days 1-7 of induction Cycle 1.

If a second cycle of induction therapy is indicated by the treating physician and the patient does not have resistant disease, it may start prior to Day 28 of induction Cycle 1 but no earlier than Cycle 1/Day 21. Dose must be recalculated if the weight changes by >10%.

Consolidation: Single-agent cytarabine will be administered at a dose of 1g/m² IV infused over 3 hours, given Q12 hours (morning and evening) on Days 1, 3 and 5. Consolidation cytarabine will be repeated every 28 days for 4 cycles unless the patient relapses, unacceptable toxicity or patient withdrawal. Dose must be recalculated if the weight changes by >10%.

16. Blood samples for PF-04449913 PK will be collected on:
 - a) Induction Cycle 1 Lead-in Day -3 at pre-dose and 1 hr post-PF-04449913 dose; b) Induction Cycle 1/Day 3 at pre-dose, 0.5 (30 min), 1, 6, and 24 hrs post-PF-04449913 dose; c) Induction Cycle 1/Day 10 at pre-dose, 0.5 (30 min), 1, 4, 6, and 24 hrs post-PF-04449913 dose; d) Consolidation cycles on Day 1 at 1 hr post-PF-04449913 dose in first 2 cycles; e) Maintenance cycles on Day 1 at 1 hr post-dose in first 2 cycles. All samples will be collected relative to PF-04449913 dosing. Refer to PK/ECG collection time points.
17. Blood samples for Cytarabine and Daunorubicin PK:

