Daunorubicin: Day 3 (Induction Cycle 1 only) at pre-dose, 0.25 (15 min, mid-infusion), 0.5 (30 min, immediately prior to the end of infusion), 1, 4, 6, 24 hrs post administration of daunorubicin. All samples will be collected relative to daunorubicin dosing. Refer to PK/ECG collection time points.

Cytarabine: Day 3 (Induction Cycle 1 only), at pre-dose, 6 and 24 hours after the start of cytarabine infusion. All samples will be collected relative to cytarabine dosing. Refer to PK/ECG collection time points.
18. Blood samples for PD biomarkers will be collected on: a) Day -3 of first induction cycle at pre-dose; b) Day 3 of first induction cycle at 1 hr post-dose; c) Day 10 of first induction cycle at 1 hr post-dose; d) Day 1 of first consolidation cycle at 1 hr post-dose; e) Day 10 of first consolidation cycle at pre-dose and f) End of Treatment. All collections are relative to PF-04449913 dosing.
19. **Type of Bone Marrow Sample:** For all patients a bone marrow aspirate and/or a biopsy sample is required and will be used for local clinical staging. **Only aspirates are required of all patients, and biopsies are optional unless required for clinical staging (e.g., dry tap).** All aspirate collections are mandatory unless in the clinical judgment of the investigator, aspirate collection is inappropriate in which case following discussion with the sponsor collection may not be required.

Time Points for Bone Marrow Sampling: For screening: An aspirate and biopsy obtained within 14 days of screening period (maximum window allowed is -42 days from study entry) is acceptable for patient eligibility and PD biomarker assessment, but if not available it will need to be obtained as part of the screening procedures.

 - **Induction:** the bone marrow samples will be collected during both Induction cycles. There is only an allowed window of +7 days (i.e., Day 21-Day 28). Bone marrow evaluations may be repeated at Investigator discretion as required for clinical staging anytime prior to next cycle of chemotherapy.

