1.2.8.2. Clinical PK Summary

1.2.8.2.1. B1371001: Patients with Selected Myeloid Malignancies

Data following single and multiple dosing of PF-04449913 from study B1371001 in patients with selected hematologic malignancies are summarized for all cohorts tested (5, 10, 20, 40, 80, 120, 180, 270, 400, and 600 mg QD).

PF-04449913 was rapidly absorbed following oral dosing with a median T_{max} of PF-04449913 ranged from 1-2 hours following a single dose and 1-4 hours following multiple dosing. The geometric mean $t_{1/2}$ for PF-04449913 ranged from 17.4 to 34.3 hours (Table 12) across the various dose levels; however, at most dose levels, the half-life was ~ 24 hours. The geometric mean CL/F ranged from 5.63 to 12.7 L/hour following a single dose and 5.33 to 13.3 L/hour following multiple dosing. PF-04449913 accumulated following repeated dosing with a median R_{ac} ranging from 1.2 to 2.5. This was consistent with the observed $t_{1/2}$, as the predicted R_{ac} is in agreement with the estimated R_{ac} . The median linearity ratio (R_{ss}) ranged from 0.76 to 2.1, with the ratio being close to unity for most of the tested dose levels.

Table 12. Summary of Plasma Pharmacokinetic Parameters Following Single and Multiple Oral Doses of PF-04449913 in Select Hematological Malignancies (Study B1371001)

Parameter (Units)	Parameter Statistics by Dose Level									
	5 mg QD n=3	10 mg QD n=3	20 mg QD n=4	40 mg QD n=4	80 mg QD n=8	120 mg QD n=3	180 mg QD n=3	270 mg QD n=5	400 mg QD n=9	600 mg QD n=5
Cycle 1 Lead-in Day (Single Dose)										
N	3	3	4	4	8 ^a	3	3	5	9 ^a	5
C _{max} (ng/mL)	32.9 (3.0)	59.0 (21)	247 (47)	313 (51)	746 (56)	1418 (22)	1409 (79)	1534 (72)	3714 (30)	4527 (64)
T _{max} (hr)	2.0 (1.0-4.0)	2.0 (1.2-2.0)	1.0 (1.0-2.0)	1.0 (1.0-1.0)	2.0 (1.0-4.0)	2.0 (1.3-4.0)	2.0 (1.1-4.0)	2.0 (1.0-4.1)	2.0 (1.3-4.5)	2.0 (1.1-4.0)
AUC _{inf} (ng•hr/mL)	657(19)	786 (23)	3548 (50)	3614 (38)	8755 (64)	14430 (35)	21280 (64)	25110 (109)	67720 (19)	86620 (58)
CL/F (L/hr)	7.61 (19)	12.7 (23)	5.63 (50)	11.1 (37)	9.13 (64)	8.33 (36)	8.48 (64)	10.8 (110)	5.90 (19)	6.93 (58)
Vz/F (L)	262 (32)	455 (41)	265 (62)	367 (38)	292 (71)	316 (52)	210 (92)	359 (143)	185 (50)	191 (78)
t _{1/2} (hr)	25.1 (9.6)	25.1 (4.3)	34.3 (14)	23.3 (4.2)	23.3 (8.1)	26.5 (4.0)	17.4 (3.3)	23.6 (5.5)	23.9 (14)	19.6 (4.7)
Cycle 1/Day 21 (Multiple Dose)										
N	3	3	3	3	5	3	4 ^c	2	6	4
C _{max} (ng/mL)	45.4 (12)	75.0 (30)	249 (35)	565 (83)	871 (35)	1621 (10)	2069 (41)	1504	4989 (7.0)	6413 (65)

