9.4.1.2.2. Combination Cohort 2 (Fit Patients): PF-04449913 and Cytarabine/Daunorubicin

The primary PK parameters, AUC and C_{max} , will be utilized to estimate the effect of coadministration of PF-04449913 and cytarabine/daunorubicin on the PK of PF-04449913. The geometric mean ratios and its 90% confidence intervals (if data permit) for the PK parameters will be used for assessment of the extent of interaction for PF-04449913 in presence of cytarabine/daunorubicin and PF-04449913 alone.

PF-04449913 AUC and C_{max} when administered alone (Induction Cycle Day 10) will be compared to Induction Cycle Day 3 AUC and C_{max} , when administered in combination with cytarabine/daunorubicin. The effect of PF-04449913 on cytarabine/daunorubicin will not be conducted within the study due to the inability to dose cytarabine/daunorubicin alone.

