8.2.7.2. Fit Cohort: PF-04449913 and Daunorubicin/Cytarabine

The primary pharmacokinetic parameters, AUC and C_{max} , will be utilized to estimate the effect of co-administration of PF-04449913 and daunorubicin/cytarabine on the pharmacokinetics of PF-04449913. The geometric mean ratios and its 90% confidence intervals (if data permit) for the PK parameters will be used for assessment of the extent of interaction for PF-04449913 in presence of daunorubicin/cytarabine and PF-04449913 alone.

PF-04449913 AUC and C_{max} when administered alone (Induction Cycle Day 10) will be compared to Induction Cycle/Day 3 AUC and C_{max} , when administered in combination with daunorubicin/cytarabine. The effect of PF-04449913 on daunorubicin/cytarabine will not be conducted within the study due to the inability to dose daunorubicin/cytarabine alone.

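### Combination Cohort 2 compares PF-04449913 Cmax and AUC between two days with different sampling times, so with no interaction the Day 3/Day 10 Cmax ratio can fall below 1 but never rise above it

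*Protocol*

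**What the plan says.** Protocol Table 4 footnote 16 gives the PF-04449913 sampling times for the two comparison days. Day 3 is "Induction Cycle 1/Day 3 at pre-dose, 0.5 (30 min), 1, 6, and 24 hrs post-PF-04449913 dose". Day 10 is "Induction Cycle 1/Day 10 at pre-dose, 0.5 (30 min), 1, 4, 6, and 24 hrs post-PF-04449913 dose". The tick marks in Protocol Table 10 agree with the footnote on both days.

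These are the two days compared. Protocol 9.4.1.2.2 states that exposure "when administered alone (Induction Cycle Day 10) will be compared to Induction Cycle Day 3 AUC" and Cmax, and SAP 8.2.7.2 says the same. The measure is set out in Protocol 9.4.1.2.2: "The geometric mean ratios and its 90% confidence intervals (if data permit) for the PK parameters will be used for assessment". Protocol 9.4.1.1 makes the parameters non-compartmental and defines Cmax as the observed maximum, so Cmax is the highest sample drawn.

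On where the peak lies, Protocol 1.2.8.2.1 says median Tmax in haematologic patients "ranged from 1-2 hours following a single dose and 1-4 hours following multiple dosing". Protocol 1.2.8.2.3 gives a median of 1 to 2 h in solid tumour patients after single and multiple doses.

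**The concern.** A within-patient ratio assumes that both days measure the same quantity. Here Day 3 has no PF-04449913 sample between 1 and 6 h, while Day 10 has one at 4 h. If the true peak falls in that gap, Day 10 may catch part of it and Day 3 cannot. The ratio then moves for a reason unrelated to chemotherapy.

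This is a systematic error, so more patients would not remove it. It could suggest that co-administration lowers PF-04449913 Cmax, or partly hide a true rise. The interaction assessment is a stated secondary objective of this cohort.

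The other combination cohorts avoid the problem. Cohort 1 (Table 2 footnote 16) and Cohort 3 (Table 11) each use one set of PF-04449913 times on both of their comparison days. Nothing elsewhere in the plan repairs Cohort 2. SAP 7.3 pairs patients, not sampling times, and its use of actual times cannot restore a sample that was never scheduled.

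**Working it through.** The documents give no sample size or precision for this ratio, so there is no stated figure to reproduce. The check puts one identical concentration profile (true ratio 1) on both sets of times.

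**Inputs from the documents.** The sampling times above; non-compartmental analysis; half-life about 24 h at most doses (geometric means 17.4 to 34.3 h, Protocol 1.2.8.2.1); bi-exponential decline (Protocol 1.2.8.2.3); 6 patients (Protocol 3.1.2). In Table 12, single-dose Tmax has median 2.0 h, range 1.0 to 4.0 h, at 80 mg, and median 2.0 h, range 1.3 to 4.0 h, at 120 mg.

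**Assumed.** Absorption and distribution constants, chosen to span those Tmax and half-life values.

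**Step 1, what holds for any profile.** Write C(t) for the concentration at t hours and M for the highest Day 3 sample. Day 10 has the same samples plus C(4), so

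Cmax ratio (Day 3/Day 10) = M / max(M, C(4)) = min(1, M/C(4)).

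It drops below 1 only when C(4) is higher than every other sample. For AUC by the linear trapezoid, the days differ only between 1 and 6 h:

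Day 3 minus Day 10 = 5[C(1)+C(6)]/2 − {3[C(1)+C(4)]/2 + 2[C(4)+C(6)]/2} = [2C(1) + 3C(6) − 5C(4)]/2.

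The sign depends on whether C(4) lies above or below the straight line from 1 h to 6 h.

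**Step 2, one-compartment profile, half-life 24 h, steady state.**

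| Tmax | Cmax ratio | AUC ratio |
|---|---|---|
| 1 h | 1.000 | 1.000 |
| 2 h | 0.991 | 0.995 |
| 3 h | 0.953 | 0.991 |
| 4 h | 0.976 | 0.989 |

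**Step 3, a two-compartment example.** Terminal half-life 23.3 h, assumed distribution half-life 4 h, ka 0.8 per h, distribution fraction 0.8; Tmax is 2.56 h. Relative concentrations at 0, 0.5, 1, 4, 6 and 24 h are 0.2155, 0.5286, 0.7153, 0.8300, 0.6972 and 0.2155.

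- Cmax ratio: 0.7153/0.8300 = 0.862.
- AUC difference: (2×0.7153 + 3×0.6972 − 5×0.8300)/2 = −0.314. Day 10 AUC is 12.556, so the ratio is 1 − 0.314/12.556 = 0.975.

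**Step 4, range over two-compartment profiles.** With distribution half-life 2 to 4 h, ka 0.3 to 4 per h and distribution fraction 0.5 to 0.8, the Cmax ratio is 1.00 for most profiles with Tmax up to about 2 h. It falls to 0.84 for Tmax of about 2.5 to 3.5 h. AUC ratios run from 0.97 to 1.02. Other assumed constants take the lowest Cmax ratio to about 0.79 and the AUC range to 0.94 to 1.05.

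**Step 5, from one patient to the reported ratio.** If k of 6 patients have ratio r and the rest have 1, the geometric mean ratio is r^(k/6). Taking r from 0.81 to 0.93 for late peaks:

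- k = 2: 0.81^(2/6) = 0.93; 0.93^(2/6) = 0.98.
- k = 1: 0.81^(1/6) = 0.97; 0.93^(1/6) = 0.99.

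**Step 6, a separate small effect.** Dosing starts on Day −3 with no Day 0, so Day 3 is dose 6 and Day 10 is dose 13. At a 24 h half-life the accumulation ratio is (1 − 0.5^6)/(1 − 0.5^13) = 0.984. Aligning the sampling times does not change this.

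**The case against.** The strongest reply concerns size and consequence, not the schedule. The 1 to 4 h figure is a range of medians across doses from 5 to 600 mg. Solid tumour patients had a median of 1 to 2 h after multiple dosing, and the single-dose median is 2.0 h at both doses bracketing 100 mg. A patient at that median shows almost no Cmax bias, partly because neither day has a 2 h sample and both miss a narrow peak there. This stands for the typical patient. It does not clear the cohort, because individual Tmax at 80 and 120 mg reached 4 h.

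A reader might infer that the reported ratio will be too low by something like 7 to 19%, the fall that ratios of 0.93 to 0.81 imply. The documents do not support that. It is a per-patient figure for late peaks, it rests on assumed constants, and the planned statistic averages over 6 patients.

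The decision impact is also limited. The objective is secondary, intervals are given only if data permit, and no threshold or dosing rule is attached. Protocol 1.2.4.4 rates the interaction potential as low. With an assumed within-patient CV of 30%, the 90% interval for 6 patients around a ratio of 1 is about 0.71 to 1.41, far wider than the likely bias. That makes the artefact less influential but does not justify keeping it when it can be removed at analysis.

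**Conclusion.** The mismatch is real, and the footnote and Table 10 agree on it, so it is not a typing error in one place. Following the plan as written gives a Cmax ratio that, with no interaction, is biased in one direction only. The direction assumes the ratio is combination over alone, the natural reading although no formula is written; inverted, the bias would be upward.

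The likely size in the reported Cmax ratio is a few percent, about 0.93 to 0.98 if 2 of 6 patients peak late. Individual late-peaking patients could show a false fall of up to about 20%. These sizes depend on assumed absorption and distribution constants and an assumed share of late peaks; the one-sidedness does not.

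A reader might also infer that AUC is seriously distorted. It is not: the shift is mostly within about 5% and can go either way. Cmax is the issue. The point is worth correcting because the correction is cheap, but it does not invalidate the interaction assessment.

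**What to change.** In SAP 8.2.7.2, state that the AUC and Cmax used in the Cohort 2 ratio are derived from the nominal times common to both days: 0, 0.5, 1, 6 and 24 h. Identical profiles then return exactly 1.000. Report the full-grid Day 10 parameters and the full-grid ratio beside it as descriptive. Add a footnote that neither ratio can show a change in a peak lying between 1 and 6 h, because Day 3 has no sample there.

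The cost is one or two sentences and a second set of parameters. The downside is that the Day 10 4 h value leaves the main ratio. The change equalises the two days; it does not recover the missing information.

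If any Cohort 2 patient is still to be sampled, add a PF-04449913 sample on Day 3 at 4 h after the PF-04449913 dose, so both days share the full grid. Footnote 17 already schedules daunorubicin draws at "1, 4, 6, 24 hrs post administration of daunorubicin", and Table 10 has patients hospitalised that day, so the burden is one 1.5 mL sample. That draw is timed from daunorubicin, which is given with PF-04449913 only where possible, so the new sample needs its own nominal time. It may come too late: Protocol 1.2.8 reports 45 of at most 49 patients treated by January 2020, without a split by cohort.

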1. INTRODUCTION

PF-04449913 is a novel small molecule inhibitor of the Sonic Hedgehog (Hh) signaling pathway being developed for the treatment of hematologic malignancies and solid tumors. This Phase 1 study is designed to evaluate the safety, tolerability, efficacy, PK and PD of PF-04449913 administered orally as a single agent in Japanese patients with select advanced hematologic malignancies, in combination with intensive chemotherapy (cytarabine and daunorubicin) or low-dose cytarabine (LDAC) in patients with previously untreated AML or high-risk MDS, or in combination with azacitidine in previously untreated AML patients who are eligible for non-intensive chemotherapy. PF-04449913 is administered as a single agent in 1 Japanese MF patient who has been treated in Study B1371013. Forty-nine patients will be enrolled in this study at maximum.

1.1. Indication

Hematologic malignancies, including acute myeloid leukemia (AML) and high-risk myelodysplastic syndrome (MDS).

1.2. Background and Rationale

1.2.1. Malignancy, Stem Cells, and the Hedgehog (Hh) Signaling Pathway

[figure not shown]
A milestone in understanding cancer as a developmental problem is the identification of cancer stem cells that self-renew, reinitiate tumor development, and give rise to tumor bulk. This may ultimately contribute to tumor resistance and metastatic spread, and impact overall survival. Standard chemotherapy, radiotherapy, and a range of targeted therapies can reduce tumor bulk, but are less effective at targeting cancer stem cells. The key challenge has been to identify the molecular mechanisms that maintain and support cancer stem cell self-renewal and survival.

Hh and Gli signaling (Hh-Gli) are critical pathways in animal patterning and cell terminal differentiation during embryogenesis, and may play a key role in human malignancies when aberrantly activated. After birth, the Hh pathway is repressed in the majority of cells but is activated during tissue repair and in self-renewing populations. Hh signaling is initiated when Hh binds to the Patched (PTCH) transmembrane protein and inactivates its function, which in the absence of Hh, is to inhibit SMO signal transduction. Following deactivation of PTCH in response to the binding of Hh ligand, the seven-transmembrane protein Smoothed (SMO), which is normally held in an inactive state by PTCH, is released and activates a signaling cascade that regulates the Gli family of transcription factors (Figure 2). The Gli family of genes encodes proteins that act either as transcriptional repressors (in the absence of Hh), or as transcriptional activators (in the presence of Hh) of genes controlled by the Hh pathway. Several proteins modulate the ratio of Gli activator (GliA) to Gli repressor (GliR) activity and in so doing determine the level of active cellular Hh ligand (Figure 2).

Since its original description, the Hh pathway has received increasing attention as a pleiotropic oncogenic pathway, and its aberrant activity has been implicated in both hematopoietic and solid tumor malignancies utilizing a range of different mechanisms, including direct cell cycle and anti-angiogenic effects (Thomas BJ, 2005; Straface G et al,

2008).^{1,2} Given that these cell types and mechanisms are unrelated in their developmental origin, site, and function, a common dependence of cancer stem cells on Hh-Gli signaling for survival and self-renewal, paralleling its roles in normal development and homeostasis, could underlie its widespread involvement in human cancers (Altaba AR, 2008).³ An important caveat is that the Hh signaling pathway is dispensable for adult hematopoietic stem cell function (Gao J et al, 2009).⁴

Figure 2. Mechanism of Hh Signaling

Cancer Cell 14, October 7, 2008 ©2008 Elsevier Inc.

1.2.2. The Role of Hh in Myeloid Malignancies

Aberrant Hh signaling has been described in a variety of different human lymphoid and myeloid leukemias, and leukemia stem cells. The expression levels of PTCH, SMO and GLI1 were found to be elevated in several leukemic cell lines (Bai LY et al, 2008)⁵. PTCH and SMO were found to be expressed in Jurkat T-ALL cells, and Shh and GLI1 expression were identified in human promyelocytic leukemia (HL-60) and KG-1 cell lines (Kobune M et al, 2009).⁶ Patient-derived AML samples have been shown to express Gli-1 in proportion to the number of CD34⁺ blast cells (Jamieson C et al, 2011).⁷ In addition, Hh signaling is up-regulated in several subtypes of human AML cells, including primary CD34⁺ leukemic cells and cytokine-responsive CD34⁺ cell lines such as Kasumi-1, Kasumi-3, and TF-1. Inhibition of Hh signaling induced apoptosis following 48 h of exposure, although these CD34⁺ cell lines exhibited resistance to cytarabine. These data were confirmed by reverse transcription-

polymerase chain reaction (RT-PCR) for Hh pathway components, and a GLI-responsive reporter assay (Kobune M et al, 2009).⁶ Finally, upregulation of Hh pathway components has been observed in chemoresistant AML cell lines in vitro, and pharmacological inhibition of the Hh pathway resulted in decreased multi-drug resistance (MDR-1) or P-glycoprotein (P-gp) expression in these cells (Queiroz KCS et al, 2010).⁸

Given the central role of Hh signaling in cell differentiation, Hh inhibition represents a mechanistically novel approach, with the potential to eliminate the leukemia stem cells (LSC) population and to abrogate tumor proliferation in at least a subset of CD34+ lymphoid and myeloid hematopoietic malignancies.

1.2.3. Role of Hh Pathway Activation in Myelodysplastic Syndrome (MDS) and Acute Myeloid Leukemia (AML)

MDS and AML comprise a group of myeloid neoplasms, whose common feature is a stem-cell-derived clonal myelopoiesis with altered proliferation and differentiation. AML is generally a disease of older individuals, and is uncommon prior to the age of 40. The average age of diagnosis of AML is 67 years. It is estimated that there will be 12,950 new cases and 9,050 deaths from AML in the United States in 2011 (American Cancer Society: Cancer Facts and Figures 2011).⁹ It is estimated that there will be 3,400 new cases of AML in Japan (Mattson-Jack Epi data 2012). Similarly, the onset of MDS before age 50 is rare, and the estimated annual incidence of MDS is similar for different regions; United States (3.3 per 100,000 persons), England and Wales (3.6 per 100,000), Germany (4.1 per 100,000) and France (3.2 per 100,000) (Rollison DE et al, 2008).¹⁰ It is estimated that annual incidence rate of MDS is 2.7 per 100,000 in Japan (Investigation by Japan Ministry of Health, Labour and Welfare). Genetic and functional studies have demonstrated that AML and MDS develop as a result of the acquisition of genetic and epigenetic alterations resulting in abnormal cell differentiation and dysregulated self-renewal.

In 2001, the WHO (World Health Organization) committee modified the FAB (French-American-British) system ([Appendix 2](#)) by lowering the level of myeloblasts required for the diagnosis of AML to >20%. The revised MDS 2008 WHO criteria ([Appendix 3](#)) made additional adjustments, classifying adult-onset primary MDS into six subcategories including RAEB-2 (defined as 5-19% circulating peripheral blasts or 10-19% bone marrow blasts). The estimated risk of leukemic transformation from RAEB-2 (also referred to as high-risk MDS) to AML is more than 50%; thus most patients with MDS RAEB-2 are treated with AML-type therapies (Tefferi A et al, 2009).¹¹

In addition to the evidence described in Section [1.2.2](#), further data supporting the importance of aberrant Hh pathway activation in leukemia is derived from patients enrolled in the completed SMO inhibitor monotherapy hematology trial (B1371001). Preliminary data from this study suggests that the mechanism of action of Hh inhibition in leukemia may involve the mobilization of blast cells from the bone marrow to the peripheral blood, with subsequent expansion and differentiation to leukemia stem cells (Jamieson C et al, 2011).⁷ Fiedler W et al (ASH 2011)¹² examined untreated AML patient samples and identified GLI2 gene expression as a negative prognostic indicator that correlated with *FLT3* mutation status. In

addition, the clinical outcome of patients correlated with Hh pathway expression, suggesting that aberrant Hh pathway activity may be a relevant therapeutic target.

Given the central role that Hh signaling plays in cell differentiation through impacting both the LSC population and the surrounding stromal microenvironment or niche supporting these cells, Hh inhibition in combination with chemotherapy represents a mechanistically attractive approach to assist with the elimination of the residual LSC population in AML and MDS that persists following standard chemotherapy regimens, and is likely to contribute to recurrence.

